Community and physician perceptions of chest pain and prevalence of acute coronary syndrome among emergency department patients in Moshi, Tanzania

Principal Investigator

[name]
Global Health Fellow
Division of Emergency Medicine
Duke Global Health Institute
[contact]
Cell [name]

Co-Investigators:

[name], PhD
Director, KCMC/Duke Collaboration
Kilimanjaro Christian Medical Center
[contact]

[name]
Assistant Professor
Division of Emergency Medicine
Duke Global Health Institute
[contact]
US cell [contact]

[name]
Professor
Division of Infectious Disease
Duke Global Health Institute
[contact]

NCT04563546

Document Date: November 5, 2024

Abstract:

Despite the rapid increase in cardiovascular risk factors across sub-Saharan Africa such as hypertension, little is known about the prevalence of acute coronary syndrome (ACS) in the region. Very few studies have described ACS in the continent, and it remains unclear whether or not the disease is rare or simply underrecognized. Possible explanations for under-detection of ACS include patient factors such as healthcare seeking behavior and physician factors such as failure to consider the diagnosis of ACS. In Tanzania, no data are available regarding the prevalence of ACS, and it is unknown to what degree patient and physician knowledge, attitude, and practices may be contributing to under-diagnosis of ACS in the country. This project will aim to explore patient and physician perceptions of chest pain and ACS, to describe the current patterns of care for patients with ACS-related symptoms in northern Tanzania, and to determine the prevalence of ACS in the emergency department in Moshi.

Abbreviations:

ACS Acute Coronary Syndrome

ED Emergency Department

ECG Electrocardiogram

HIC High Income Countries

ICER Incremental Cost Effective Ratio

KAP Knowledge, Attitude, and Practice

KCMC Kilimanjaro Christian Medical Center

LMIC Low and Middle Income Countries

WHO World Health Organization

Introduction:

Acute coronary syndrome (ACS), colloquially known as the “heart attack,” is a leading cause of morbidity and mortality from poorly controlled hypertension ¹. In sub-Saharan Africa, ACS has long been considered of less importance due to the relatively high burden of communicable diseases ². In recent years, however, countries across sub-Saharan Africa have faced a sharp increase in ACS risk factors, such as longer life span, reduced exercise, poor diet, hypertension and diabetes ³. Given the well-documented rise of these risk factors in the region, several authors have highlighted the increased need for accurate data regarding the burden of disease of ACS in sub-Saharan Africa ⁴. This study will determine the prevalence of ACS in the emergency department setting in northern Tanzania and assess patient and physician beliefs and practices which may be contributing to a low rate of ACS diagnosis.

Literature Review:

Despite the need for data regarding ACS prevalence, very little is known about the burden of ACS across the African continent. Our team’s recent systematic review found there are very few studies on the incidence of ACS in sub-Saharan Africa; studies were mostly performed in small, narrowly-defined patient populations and were generally of low quality ⁵. None of these studies were performed in Tanzania. Based on the sparse data available, however, researchers have pointed out that the incidence of ACS in the region seems to be much lower than what would be expected given the local prevalence of ACS risk factors ⁶. It remains unclear whether or not ACS in sub-Saharan Africa is actually a rare phenomenon, or just an under-reported one.

There are many possible explanations for the apparent relative scarcity of ACS in sub-Saharan Africa. One such explanation is related to care-seeking behavior. Since most data regarding ACS incidence comes from hospital-based studies, if large numbers of patients do not present to a hospital for symptoms such as chest pain, then the local incidence of ACS may be significantly under-reported. In developed countries, there is already ample evidence that care-seeking behavior for patients with ACS symptoms is significantly affected by socioeconomic factors, health literacy, and cultural factors ⁷. It is unknown to what extent, if any, similar factors are affecting patient healthcare seeking behavior, and in turn, under-reporting of ACS in Tanzania.

Physician beliefs and practices may also be contributing to under-diagnosis of ACS. If physicians do not consider the diagnosis of ACS or do not pursue diagnostic workups (such as ECGs) for patients with symptoms suggestive of ACS, their behavior may be reinforcing a misperception that ACS is a relatively uncommon and unimportant disease in the region. Studies performed elsewhere in sub-Saharan Africa have shown that physician beliefs and practices contribute to misdiagnosis and inappropriate treatment for infectious syndromes ⁸. The degree to which physician practices may be similarly contributing to under-appreciation of ACS in Tanzania is unknown.

Statement of the Problem:

Little is known about the prevalence of ACS in sub-Saharan Africa or the ways in which patient and physician practices may be affecting detection of this disease.

Rationale:

This project will gather information in order to determine the prevalence of ACS in emergency department in Moshi, Tanzania. Patient and physician perceptions and practices which may be contributing to ACS under-diagnosis will also be explored.

Broad Objective:

To determine the prevalence of ACS among adults in the emergency department.

Specific Objectives:

Specific Objective 1: To explore the knowledge, attitudes, and practices (KAP) of community members and physicians regarding ACS and ACS-related symptoms in northern Tanzania.

Specific Objective 2: To determine the prevalence of ACS-related symptoms in an emergency department in northern Tanzania and describe current patterns of care for such patients.

Specific Objective 3: To determine the prevalence of acute myocardial infarction in an ED population in northern Tanzania.

Methods:

Setting: Moshi is located in the Kilimanjaro region of Northern Tanzania. It has a population of 184, 292 people and includes both Moshi Rural and Moshi Urban. It is home to Kilimanjaro Christian Medical Center (KCMC) which is a referral hospital for northwestern Tanzania and a regional training center. Duke and KCMC have developed a research infrastructure with proven success in NIH funded grants. Many successful research projects have been conducted through the Casualty department with the help of an experienced team of Tanzanian research nurses and data entry technicians.

Study Design: The prevalence of ACS will be ascertained with a cross-sectional survey of a representative sample of all casualty department patients presenting with chest pain or shortness of breath. The prevalence of acute myocardial infarction will be determined by obtaining electrocardiograms (ECGs) and point-of-care troponins on all patients presenting with symptoms suggestive of ACS. Quantitative data concerning ACS knowledge and barriers will be obtained by patient knowledge, attitude, and practice (KAP) surveys. Qualitative information regarding barriers to care, healthcare seeking behaviors, and management of ACS will be obtained using patient focus groups and in-depth interviews with ED providers.

Study Population: All participants will be >17 years of age and be able to speak Swahili (patients or families) or English (healthcare practitioners). We will exclude patients with an inability to respond to the survey due to the severity of their illness or injury. We plan to enroll 500 patients in the observational study of patients with ACS-related symptoms and 500 patients in the ACS prevalence study.

Inclusion/ Exclusion Criteria:

Patients will be included in the prospective observational study of ACS-related symptoms and prevalence of myocardial infarction study if they have a primary or secondary chief complaint of chest pain or shortness of breath. All patients must be >17 years of age, be seeking care at KCMC in the casualty department, be clinically sober at the time of enrollment, be able to communicate in Swahili or English and consent to participate. Patients will be excluded from enrollment if they are medically unstable or have a deteriorating condition, are too critically ill to participate, are <18 years of age.

Sample Size Calculation:

Reported prevalence of myocardial ischemia among various African sub-populations (not general ED populations presenting with chest pain) range from 0.2%⁹ to 10.4%¹⁰. Assuming the prevalence of ischemic ECGs among ED patients with chest pain will be at the high end of this range (10%), then 210 patients will need to be enrolled in order to report this prevalence with a precision of +/- 5%.

The proportion of ED patients with chest pain in Tanzania is unknown, but in developed settings is typically around 10%.^{11, 12} Assuming a similar proportion of patients will be eligible for inclusion in our study, and given current patient volumes at KCMC (25 adults/dayshift), enrollment will need to be conducted for 5 months to achieve the desired sample size.

Instruments/Procedures:

KAP (Specific Objective 1): A focused knowledge, attitude, and practice survey (KAP) survey will be developed, adapting questions from existing cardiovascular KAP surveys used elsewhere¹³⁻¹⁶. The survey will piloted on a small sample (N<20) of persons (who will be excluded from the final study) in order to report upon the internal consistency or reliability of the survey in Kiswahili and to assess the content validity of the survey in Kiswahili. It will be necessary to audio record the pilot interview sessions in order to allow for complete translation into English. Participants will not be identified by name on the tapes, and all recordings will be discarded after translation. This pilot will occur before the start of the study recruitment. After acceptability is assured the survey will then be given to all patients enrolled in the study.

Focus Group Methodology (Specific Objective 1): Focus groups will be held in Swahili with patients to better assess their understanding of chest pain and acute coronary syndrome, adherence with treatment, and any cultural barriers or culturally relevant solutions for a successful intervention and follow-up plan. Community members from randomly selected communities in Moshi Urban or Moshi Rural will participate in the focus groups. All patients who agree will be included until 3-4 focus groups are complete with a minimum of 10 participants each. Patients will be offered transportation money if they elect to return for focus groups. The focus groups will occur in a small quiet room near to the Casualty Department or in the local community.

In-depth Interview Methodology (Specific Objective 1): Approximately twenty in-depth interviews with a semi-structured format will be conducted in English or Swahili with casualty department physicians to assess their current practice surrounding the management of ACS in the emergency department. Implied consent language will be utilized. These conversations will be recorded and transcribed.

Retrospective Chart Review (Specific Objective 2): Patient logs from the Emergency Department for a six-month period prior to study initiation date will be reviewed. From these logs, data will be collected including patient age, sex, and diagnosis. No identifying information such as name or date of birth will be collected. This data will allow for an analysis of current patterns of ACS-related diagnoses in the ED.

Prospective observational study of patients with ACS-related symptoms (Specific Objective 2): A triage system in the KCMC ED is about to be implemented to improve quality of care. The triage nurse, as part of routine care, will begin obtaining all five vital signs (blood pressure, heart rate, temperature, respiratory rate, and oxygen saturation). Patient complaints will be entered into a triage registry, along with patient age, sex, and vital signs. This registry data will be collected for our research purposes. No identifying information will be entered into this registry or our data collection. This triage registry will act as a quality improvement initiative to evaluate the triage process in the ED. As this registry will become part of routine care as a quality improvement project for the ED, patients will not undergo informed consent to have their vital signs and chief complaints in the triage registry. The de-identified data from this registry will be used to determine the prevalence of ACS-related chief complaints such as chest pain and shortness of breath among emergency department patients. This registry will be screened and patients presenting with a primary or secondary complaint of chest pain or shortness of breath will be enrolled for this prospective observational study. The ACS Patient survey (attached below) will be administered to all participants. Patients will be followed through their emergency department stay; their diagnostic workup, treatment, diagnosis, and disposition will be observed and recorded.

ACS prevalence study (Specific Objective 3): Following the observational study, all adult patients presenting to the KCMC Emergency Department with a primary or secondary complaint of chest pain or shortness of breath will be prospectively enrolled in the prevalence study. At time of enrollment, these patients will undergo testing with ECG and point-of-care troponin level, and a second point-of-care troponin level will be obtained two hours later. The results of

these studies will be shared with the clinical team. The ECGs will be reviewed by two separate physicians, trained in either emergency medicine or cardiology to determine whether or not the ECG meets STEMI criteria. If there is a disagreement, a third physician will serve as the tiebreaker.

Survey Data Collection: Data will be collected on tablets and stored in a secure database by a trained data entry technician. Surveys for all components of this study will be verbally administered to patients and families due to variable literacy rates. They will be administered by healthcare providers in the standard medical language of English or Swahili. Results of urine dipstick will be recorded for the presence or absence of proteinuria. Results of troponins will be recorded and digital images of ECGs will be uploaded. Phone number of the patient and will be recorded in the log and de identified. No PHI will be entered into Redcap or any study database. The log will remain in a secure, locked cabinet the research office.

Focus Group Data Collection: Participants will take part in an informed consent process approved by the Duke and Tanzanian ethics committees before joining the focus group that is included in the survey consent form. Focus groups will be formed once 5-10 eligible interested participants are identified. Focus groups, led by trained research nurses or other trained research personnel, will be audiotaped and transcribed for formal qualitative analysis utilizing thematic analyses. Transcriptions will occur within four days of the focus group and research nurse notes will be included in these transcriptions about the content. We expect to host approximately 3-4 focus groups.

Data Analysis: Survey results will be analyzed through analytical techniques. Continuous variables will be reported as mean and standard deviation (SD) or median and inter-quartile range (IQR). Pertinent outcome variables are expected to be dichotomous. (e.g., tobacco use, gender, alternative medicine use).

Focus Group/In-Depth Interview Data Analysis: After transcription, each of the focus groups and in-depth interviews will be translated and the final transcript will be discussed by the research nurses present in the focus group for content validation. Then a thematic analysis will be undertaken for each of the main questions from the focus groups/in depth interviews. All data will be analyzed with NVivo 10.0. Latent Semantic Analysis and Sentiment Analysis will be used to investigate latent concepts or positive/negative tones behind the qualitative answers. All transcripts, audiotapes and other study documents will be kept for 6 years following conclusion of the data the conclusion of the study.

Study Timeline: The first steps of the project included IRB submission and planning which is currently ongoing. IRB approval has already been obtained from both NIMR (National Institute of Medical Research) in Tanzania and the KCMC IRB. Data collection will occur from July 2018 – June 2019, followed by data analysis and manuscript publication.

Investigators:

[name] is a co-investigator and the onsite research director at KCMC she will ensure that the study is carried out with fidelity. As a native swahili-speaker, medical provider,

and clinical researcher, she will provide critical cultural and clinical expertise. She will additionally be relied on throughout the project to assist with any cultural and language issues that may arise at later stages of the project.

[name] is a co-investigator. He will assist with project planning, implementation, data analysis, and manuscript preparation.

[name] is a co-investigator. She will also assist with study design, study oversight, data analysis, and manuscript preparation.

[name] is a co-investigator. He will also assist with study design, study oversight, data analysis, and manuscript preparation.

Ethical Considerations:

Capacity Development:

This project was based on the local needs, available resources and standard practices in the KCMC Emergency Department. We have sought out collaborators both at Duke as well as at KCMC and have adapted our project to their suggestions and experiences. We will employ and train, [name], a Masters student in sociology at the Open University of Tanzania, who has considerable experience performing focus groups with the Duke-KCMC research collaboration. He will oversee both the focus groups and the administration of the KAP survey. We will continue to recruit junior faculty at KCMC to assist with all research concerns and plan to collaborate with [name], nephrologist and chair of the internal medicine department at KCMC for future publications and research project.

Subject Recruitment and Compensation:

All patients at KCMC Casualty Department who meet inclusion criteria will be offered enrollment in the study. The only cost to participants is the time spent performing the survey. The participants will not be compensated for their time for this study. Participants will not be compensated for their time spent completing the survey. They will be compensated for travel and food if they return for focus groups.

Consent Process:

For patients we will be utilizing a written informed consent. Participants will be provided with a description of the study objectives and procedures, along with information on data safety. Agreement to participate in the survey will serve as consent to participate in the study. The in-depth interviews will have an implied consent language. The participants will be enrolled by study nurses.

Dissemination and Publications:

Dissemination of results will occur for both the academic literature in the form of international presentations and research manuscripts as well as the clinical environment at KCMC. We will offer to KCMC leadership to discuss our results during the weekly Clinical Case Conference in order to educate KCMC Clinicians. Similarly, presentations in the Casualty Department will take place for KCMC Casualty Department staff and all healthcare providers. We also hope to share these results with emergency department providers and health policy officials in order to understand the burden of disease suffered by our patients in hopes of planning for the needs of healthcare professionals for these patients.

Budget:

Item	Cost in US Dollars
RN time x 12 months	9,600
RN data/internet time x 8 months	500
Printing .13 x sheet	3328
Automatic BP cuff x 2	100
Alcohol pads (1/per subject)	donated
POC troponin machines	donated
EKG paper	donated
ECG machines	donated
Patient focus group transportation/food/time x 100 subjects	300
MD indepth interview food x 3	100
KCMC overhead 10% total budget	3213
Total	15,321

Budget Justification:**PERSONNEL**

Research nurse: One full time research nurse will be required for all the aims of this study.

They will be employed according to the research project requirements and will be active on other projects thus supplementing their salary during periods when less participant contact is needed.

The research nurses will be responsible for recruiting patients for the surveys, follow-up groups and performing blood pressure measurements, ECGs, and troponins. They will also be responsible for informed consent of participants, conducting all interviews, maintaining participant files, and communicating progress to [name]. Nurses will be paid \$800 per month, which is standard for Duke/KCMC Collaboration research nurses. One nurse will be full-time for 12 months (\$9,600).

SUPPLIES:

Laboratory equipment: One alcohol pad will be required for each patient and these supplies will be donated.

Two automatic blood pressure cuffs will be needed. (\$100) ECG machines, POC troponin machines, and cartridges will be donated.

Paper and printing costs: (\$3,328) We request funds in order to cover paper and printing costs for the project. Informed consent, surveys and any regulatory paperwork will need printing estimating 16 pages/participant x 1600 participants at 25,600 pages at 0.13 cents for paper and printing costs. Total funds requested \$3,328.

Patient focus group transportation and food: Ten focus group will be held x 10 patients each. Each participant will be reimbursed (5,000 TSH)= (\$3USD) for transportation plus food.(\$300)

In-depth interview: Interviewee will be paid for their time and provided with a meal. (\$100)

KCMC overhead According to our funders, the US National Institute of Health guidelines, we are requesting 10% of the total KCMC budget be paid to the Good Samaritan Foundation account at KCMC hospital for the privilege of being housed at KCMC and other administrative costs.

References

1. WHO | A global brief on hypertension. *WHO*. 2013.

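### The broad objective is ACS prevalence among ED adults, but the tested figure is AMI prevalence among enrolled adults with chest pain or dyspnoea, and no planned step gives a tested ED-wide estimate

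*Combined protocol and SAP*

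**What the plan says.** The target is stated widely. The Broad Objective is "To determine the prevalence of ACS among adults in the emergency department", and the Abstract says the project aims "to determine the prevalence of ACS in the emergency department in Moshi". Specific Objective 3 changes the condition and leaves the population open: "To determine the prevalence of acute myocardial infarction in an ED population in northern Tanzania".

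The methods are narrower. Study Design says "The prevalence of ACS will be ascertained with a cross-sectional survey of a representative sample of all casualty department patients presenting with chest pain" and adds shortness of breath as the alternative complaint. ECG and troponin are assigned there to AMI, in patients whose symptoms suggest ACS. Under Inclusion/ Exclusion Criteria, "Patients will be excluded from enrollment if they are medically unstable or have a deteriorating condition, are too critically ill to participate"; patients must also consent, be sober and speak Swahili or English. Study Population plans "500 patients in the ACS prevalence study". Under Instruments/Procedures, ECGs are adjudicated for STEMI criteria.

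Three other sources bear on the question, all under Instruments/Procedures for Specific Objective 2:
- The triage registry records complaints, age, sex and vital signs. It is used to estimate how common ACS-type complaints are among ED patients.
- The retrospective review of ED logs collects age, sex and recorded diagnosis over six months.
- The observational study records clinicians' work-up and diagnosis in symptomatic patients.

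Data Analysis covers descriptive summaries and dichotomous variables. It gives no prevalence estimator and no step that joins the registry share to the test results.

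**The concern.** The stated question and the tested answer differ in condition (ACS against AMI) and in denominator (all ED adults against enrolled symptomatic adults). The study exists to find out whether ACS is rare in the region or under-recognised. The only planned diagnosis figure that covers the whole ED comes from the logs, and the Literature Review gives the reason to distrust it: "Physician beliefs and practices may also be contributing to under-diagnosis of ACS". The tested figure avoids that problem but covers a subgroup. A plan followed exactly would therefore report no tested ED-wide figure, and a reader who set the subgroup figure against the Broad Objective would take it for one.

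**Working it through.** **1. What each source delivers**

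| Source | Condition | Who is covered | Systematic study testing? |
|---|---|---|---|
| Prevalence study | AMI | Enrolled adults with chest pain or dyspnoea | Yes |
| Observational study | Clinician's diagnosis | Enrolled adults with the same complaints | No |
| ED-log review | Recorded diagnosis | Whole ED | No |
| Triage registry | Complaint only | Whole ED, with age | No |

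No row combines AMI testing with the whole ED.

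**2. The plan's own figure.** Sample Size Calculation gives 210 patients for a 10% prevalence to within 5 points. It states no method or confidence level. The simple 95% formula gives 1.96² x 0.10 x 0.90 / 0.05² = 138.3, so 139. Exact (Clopper-Pearson) 95% limits with a whole-number count at exactly 10% reproduce 210: 21/210 has limits 6.30% to 14.88%, while 20/200 has an upper limit of 15.02%. So 210 is reproducible, but it is the precision of ischemic ECGs among chest-pain patients, not of an ED-wide prevalence.

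**3. Size of the possible misreading**

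Inputs:
- p = 10%, prevalence in those enrolled. This is illustrative, since the plan's 10% is for ischemic ECGs.
- f = 10%, the share the plan uses for eligibility. Its source is chest pain alone in developed settings. The values 20% and 30% are assumptions.
- e = share of symptomatic adults enrolled; r = prevalence in the rest divided by p; q = prevalence in other ED adults. All three are assumptions.

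ED prevalence = f x p x (e + (1 - e) x r) + (1 - f) x q. The fold difference is p divided by this.

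| Case | f = 10% | f = 20% | f = 30% |
|---|---|---|---|
| q = 0, r = 1 (gives 1/f) | 10 | 5 | 3.3 |
| q = 0, e = 0.8, r = 0.5 | 11.1 | 5.6 | 3.7 |
| q = 0, e = 0.8, r = 2 | 8.3 | 4.2 | 2.8 |
| q = 1%, r = 1 | 5.3 | 3.6 | 2.7 |

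For example, at f = 10% and q = 1%: 0.10 x 0.10 + 0.90 x 0.01 = 1.9%, and 10 / 1.9 = 5.3. Since 1/f is exceeded in the second row, it is not a ceiling.

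**4. What the added estimate would give.** The product is f x p. By the delta method, SE = f x p x sqrt((1 - p)/(n x p) + (1 - f)/(N x f)), with n = 500 tested and N registry adults. If all symptomatic adults are enrolled, N = 500/f.
- f = 10%, N = 5,000: 0.01 x sqrt(0.0180 + 0.0018) = 0.00141; x 1.96 gives 1.0% +/- 0.28 points.
- f = 20%, N = 2,500: 0.02 x sqrt(0.0180 + 0.0016) = 0.00280; 2.0% +/- 0.55 points.
- f = 30%, N = 1,667: 0.03 x sqrt(0.0180 + 0.0014) = 0.00418; 3.0% +/- 0.82 points.

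With f treated as known, the half-width at f = 10% is 0.26 points, so registry sampling error adds little. With 80% enrolled and half or twice the prevalence in the rest, the point estimate ranges from 0.9% to 1.2%, 1.8% to 2.4% and 2.7% to 3.6% respectively.

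**The case against.** The best defence is that the narrower population is disclosed. Study Design, the eligibility criteria, the sample size and the prevalence-study procedure all limit the work to symptomatic patients, and the indefinite wording of Objective 3 can be read that way. On this view, only a loosely worded objective needs editing. Both components of the product are also planned outputs, so anyone could multiply them later.

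Much of this stands. The subgroup estimate needs no repair, and nothing in the documents says it will be reported as ED prevalence. But the Broad Objective and the Abstract still promise something the design does not deliver. A later multiplication by a reader would also lack matched registry counts, an interval and a stated assumption about patients not enrolled.

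Three other objections limit the remedy and are accepted:
- The product covers AMI presenting with two complaints. It leaves out ACS without infarction and AMI without those complaints.
- The registry fields listed do not include arrival date or shift, and the prevalence study follows the observational study under which the registry is described. Matched extraction is therefore an assumption.
- Symptomatic adults not enrolled mix refusals with unstable patients, whose prevalence may differ in either direction. The half-to-twice range is illustrative and has no source in the documents.

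It is also fair to say that the procedures describe STEMI adjudication but no rule combining ECG and troponin into an AMI case. That is a separate gap, and it affects the subgroup estimate and the product alike.

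**Conclusion.** The mismatch is in the text and should be fixed. The plan tests for AMI in enrolled adults with chest pain or dyspnoea, while its Broad Objective is ACS in all ED adults, and nothing planned gives a tested ED-wide figure.

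The size is conditional. If the subgroup figure were taken as ED prevalence, it would be about 1/f too high: 10-fold at the plan's 10% share, and 5- or 3.3-fold at assumed shares of 20% or 30%. This holds if other adults have no AMI and symptomatic adults not enrolled have the same prevalence as those enrolled. Because the 10% refers to chest pain alone, f for either complaint is probably larger and the factor smaller.

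A reader might infer two stronger conclusions. One is that the study's estimate is biased tenfold. The documents do not support this: the fold figures measure a reader's error under assumed inputs, and the estimator is valid for its own group. The other is that multiplying by the registry share would answer the Broad Objective, or at least bound it from below. It would do neither, because the testing does not measure all ACS, and because the product exceeds the true value if symptomatic adults not enrolled have lower prevalence and few other adults have AMI.

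**What to change.** 1. Restate the Broad Objective and Specific Objective 3 as AMI prevalence among ED adults with chest pain or shortness of breath, whether primary or secondary, estimated from those enrolled. Say that the testing does not measure all ACS.

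2. Add a secondary estimate to Data Analysis: AMI presenting with these complaints per ED adult = AMI proportion x registry share of adults with these complaints, with a delta-method or bootstrap 95% CI.
   - Use registry counts for the prevalence-study period, matched to enrolment shifts if the registry records time. Otherwise state the mismatch as a limitation.
   - Report how many symptomatic adults were not enrolled (registry count minus enrolled), state the equal-prevalence assumption, and give an illustrative sensitivity range such as half and twice.
   - Present the result as a partial ED-wide figure that omits ACS without infarction and AMI without these complaints. Do not present it as the answer to the ACS question or as an unconditional lower bound.

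The cost is a registry extraction, one calculation and one subtraction. Enrolment, testing and sample size do not change. Study Timeline planned data collection for July 2018 to June 2019; if it has ended, the change still applies to analysis and reporting, provided registry counts for the period were kept. The downside is that the ED-wide figure is smaller and rests on a stated assumption about patients not enrolled.
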